# 9.5 OVAPRENE™ PCT CYCLES, WITH ASSESSMENT OF SAFETY, RELEASE, ACCEPTABILITY, AND FIT – DEVICE IN PLACE, ONE ACT OF INTERCOURSE WITH PCT IN EACH CYCLE

# **Table 10: Ovaprene™ PCT Cycle Endpoints**

Primary:	c) Proportion of women and cycles with an average of fewer than 5 progressively motile sperm per

 
Changes in
 
	HPF in cervical mucus sample, in the presence of the device.
PCT results	d) Mean, median, standard deviation and interquartile range (IQR) for the average number (across 9
due to device	HPFs) of progressively motile sperm per HPF, across all women and cycles, in the presence of the
use	Ovaprene™ device.
	e) Change from baseline in the mean, median, standard deviation and interquartile range (IQR) during each Ovaprene™ test cycle, across all women and cycles.
Secondary:	a) Levels of ferrous gluconate in CVF before sex that are associated with fewer than 5 progressively
2. Release of	motile sperm per high powered field (HPF) in cervical mucus after sex (i.e. success), during ovulation.
active	c) Levels of ferrous gluconate in CVF before and at multiple time points after sex at ovulation with the
component	device in place. (Allows determination of whether they are different from before sex and, if so, how
from device	much time is needed to return to pre-sex levels.)
	d) Cervicovaginal pH before and after sex in the absence and presence of the device.
	e) Residual amount of ferrous gluconate in Ovaprene™ devices that have been worn over a cycle of
	use.
3. Safety	a) Treatment-emergent AEs among female participants during Ovaprene™ use
	b) Urogenital, product-related, and/or serious AEs among female and male participants during
	Ovaprene™ use
	d) Changes from baseline in findings on pelvic exam, including colposcopy
	e) Changes from baseline in:
	Nugent score and microflora
	Antibacterial (anti-E. coli) activity in CVF
	Soluble markers of inflammation in CVF
	f) Presence of Staphylococcus aureus or group A Streptococcus on Ovaprene™ devices that have been
Tortione	worn over a cycle of use  a) Responses on acceptability questionnaire/diary
Tertiary: 4. Acceptability	
 
Problems with insertion, including confirmation of placement
 

4. Acceptability	
 
Aspects liked most and least by the female partner
 

	
 
Dislodgements reported by the female partner
 

	
 
Comfort reported by both partners during intercourse and whether discomfort, if reported,
 

	was bothersome and would keep the person from using the device again
5. Fit	b) Proportion of participants who can correctly insert, position, and remove the device using written
	instructions only.
	c) Proportion of participants who require assistance to correctly insert, position, and remove the device.
	d) Location of Ovaprene™ in relation to the cervix as determined by clinical exam; relationship of
	position to PCT results, safety, and acceptability.

# 9.5.1 Ovaprene™ PCT Cycle - Visits and Procedures:

#### a) Visit OP1, the day following the end of menses (approximately cycle day 6):

• Diary review, AEs, medications, and indications for a directed physical exam, wet mount, and other tests will be managed as described for Visit 2 (BP1).

Version: 06.00 (FINAL) Date: June 13, 2019

- The participant will be asked whether she used non-spermicidal, lubricated condoms
  from the onset of menses in this cycle. If instructions were not followed, she will be
  reinstructed. If she used a spermicide or spermicidal lubricated condom, Visit OP1 will
  be rescheduled in the next cycle. Otherwise, the visit may continue at the
  investigator's discretion.
- The participant will undergo a pelvic exam:
  - o Signs of irritation of the external genitalia, cervix, and vagina, as observed with the naked eye, will be noted.
  - o A colposcopic exam will be completed.
  - o Cervical mucus will be collected for pH and ferrous gluconate.
  - o Vaginal sample(s) will be collected for pH, ferrous gluconate, Nugent score, microflora, antibacterial activity, and soluble markers.
- The participant will insert Ovaprene™ using written instructions, with assistance if needed. The clinician will check the placement.
- An ovulation predictor kit (OPK) with instructions will be dispensed.
- The participant will be instructed as follows:
  - Begin daily urine testing on day 10 of that cycle (adjusted as needed to normal cycle length) and contact the study coordinator when the OPK test yields a "high" result. Visit OP2 (the mucus check visits) will then be scheduled for that day or the next day.
  - O Until day 10, she and her partner should use condoms for each act of intercourse. There should be no intercourse or other vaginal activity,s and her male partner should not have an ejaculation, starting on day 10 until after Visit OP3.

#### b) Visit OP2, the CMC visit, on the day of the "high" result or the next:

- Diary review, AEs, medications, and indications for a directed physical exam, wet mount, and other tests will be managed as described for Visit 2 (BP1).
- The participant will be asked whether she used condoms until Day 10 and then refrained from intercourse and the use of intravaginal products, and whether her male partner refrained from ejaculation since Day 10. If instructions were not followed, she will be reinstructed. If she used a spermicide or spermicidal lubricated condom since day 10, Visit OP2 will be rescheduled in the next cycle. Otherwise, the visit may continue at the investigator's discretion.
- The participant will undergo a pelvic exam:
  - o Signs of irritation of the external genitalia, cervix, and vagina, as observed with the naked eye, will be noted.

<sup>s "Other vaginal activity" includes insertion of vaginal medications/products other than the study product (prescription or over-the-counter), as well as insertion of sex toys, fingers, or anything else into the vagina. Tampons may be used during all days of menses in the Baseline PCT and Caya PCT cycles, but only during the first three days of menses in Ovaprene cycles.

Version: 06.00 (FINAL) Date: June 13, 2019

- o The position of the device relative to the cervix will be noted.
- o Cervical mucus will be examined for pH, ferrous gluconate, midcycle characteristics, and the presence of sperm (see **Appendix 2**).
- o Vaginal sample(s) will be collected for pH, ferrous gluconate, and the presence of sperm.
- o It is expected that the cervical mucus could be thick and should be without sperm at the CMC. If sperm are found in the vagina or cervical mucus, this cycle will be rescheduled and instructions on condom use and abstinence will be reviewed.
- o If no sperm are detected in the vagina or cervical mucus, the participant will be instructed to have intercourse without a condom but with the device in place, 2 to 3 hours prior to the next visit, which will be scheduled for the same or following day, within 27 hours of the mucus check visit.
- o The participant will be instructed to otherwise avoid any other vaginal activitiest until after Visit OP3.

# c) Visit OP3, the PCT visit, 2-3 hours after intercourse and within 27 hours of the CMC:

The participant will return to the clinic 2-3 hours after coitus ends and within 27 hours of the mucus check visit.

- Diary review, AEs, medications, and indications for a directed physical exam, wet mount, and other tests will be managed as described for Visit 2 (BP1)
- An acceptability questionnaire will be administered.
- The participant will undergo a pelvic exam:
  - o Signs of irritation of the external genitalia, cervix, and vagina, as observed with the naked eye, will be noted.
  - o The position of the device relative to the cervix will be noted.
  - o Cervical mucus will be examined for pH, ferrous gluconate, midcycle characteristics, and the presence of sperm (see **Appendix 2**).
  - o Vaginal sample(s) will be collected for pH, ferrous gluconate, and the presence of sperm.
  - o At sites other than EVMS, vaginal samples will be collected for antibacterial activity and soluble markers.
  - Results of the test PCT will be interpreted as shown in Appendix 3. A successful test PCT will show mucus containing an average of <5 progressively motile sperm per HPF.
- At the EVMS site only:
  - o At 0.5, 1, 2, 4, and 6 hours after the PCT: u
    - Vaginal sample(s) will be collected for pH and ferrous gluconate.
  - o At 6 hours after the PCT, if possible:

<sup>t "Other vaginal activity" includes insertion of vaginal medications/products other than the study product (prescription or over-the-counter), as well as insertion of sex toys, fingers, or anything else into the vagina. Tampons may be used during all days of menses in the Baseline PCT and Caya PCT cycles, but only during the first three days of menses in Ovaprene cycles.

<sup>u Samples will be collected at as many of these timepoints as possible.

Version: 06.00 (FINAL) Date: June 13, 2019

- Vaginal sample(s) for antibacterial activity and soluble markers will be collected.
- The participant will be instructed to refrain from intercourse and other vaginal activity until after Visit OP4, 24 hours after Visit OP3.

#### d) Visit OP4, 24 hours after the PCT:

- Diary review, AEs, medications, and indications for a directed physical exam, wet mount, and other tests will be managed as described for Visit 2 (BP1).
- The participant will undergo a pelvic exam:
  - o Signs of irritation of the external genitalia, cervix, and vagina, as observed with the naked eye, will be noted.
  - o The position of the device relative to the cervix will be noted.
  - o Vaginal sample(s) will be collected for ferrous gluconate and pH.
- Participants will be instructed as follows:
  - o Intercourse is permitted after this visit for the rest of this cycle with the following restrictions:
    - Condoms lubricated with something other than nonxynol-9 must be used (dispense as needed).
    - No sex or other vaginal activitym is permitted in the 72 hours prior to the final visit in the cycle.
  - O A tentative appointment will be made for the next visit, taking into account the participant's usual cycle length and the need to have that visit take place before the participant's next menses begins but as late as possible in the cycle. The participant will be instructed to contact the site immediately if it appears that her menses is starting before the tentatively scheduled appointment.

#### e) Visit OP5, approximately cycle day 28 or sooner if menses is expected to begin:

- Diary review, AEs, medications, and indications for a directed physical exam, wet mount, and other tests will be managed as described for Visit 2 (BP1).
- The participant will undergo a pelvic exam:
  - o Signs of irritation of the external genitalia, cervix, and vagina, as observed with the naked eye, will be noted.
  - o The position of the device relative to the cervix will be noted.
  - Vaginal sample(s) will be collected for ferrous gluconate, pH, Nugent score, microflora, antibacterial activity, and soluble markers.
  - o Ovaprene™ will be removed and stored for later analysis.
  - o A colposcopic exam will be completed.
  - o Cervical mucus will be collected for ferrous gluconate and pH.
- If this was the participant's **first** Ovaprene™ PCT cycle, she will undergo a second Ovaprene™ PCT cycle. She will be instructed to:

Version: 06.00 (FINAL) Date: June 13, 2019

- Call at the onset of her next menses to tentatively schedule Visit OP1 on the day following the end of menses. Adjustments to this visit will be made as needed.
- o Use non-spermicidal, lubricated condoms (dispense as needed) from the first day of her next menses until day 10 of that cycle, and to abstain from intercourse and other vaginal activity starting on Day 10 until after Visit OP2, the CMC visit.
- If this was her **second** Ovaprene™ PCT cycle, she will be contacted 7-10 days after this visit to assess AEs, and will be exited after this contact, unless she has symptoms requiring follow-up.

<sup>v "Other vaginal activity" includes insertion of vaginal medications/products other than the study product (prescription or over-the-counter), as well as insertion of sex toys, fingers, or anything else into the vagina. Tampons or menstrual cups may be used during all days of menses in the Baseline PCT and Caya PCT cycles, but only during the first three days of menses in Ovaprene cycles.

Version: 06.00 (FINAL) Date: June 13, 2019

Table 11: Ovaprene™ PCT Cycle Schedule (in a hypothetical woman with a 5-day menses and a 28-day cycle)

Cycle Day	1		3 4			7	8	9	10	11	12	13	14	15	16	17	18	19	20	21	)	22	23	24	25	26	27	28
Menses	М	М	МК	1 N	1																							
Ovaprene™					✓	✓	✓	✓	✓	✓	✓	✓	✓	✓	✓	✓	✓	✓	✓	✓		✓	✓	✓	✓	✓	✓	✓
ОРК									✓	✓	✓	√ high	√ peak															
Visit OP1:																												

 
Colposcopy
 
																												

 
Cervical mucus for pH & FG
 
																												

 
Vaginal samples for pH, FG, Nugent score, microflora, antibacterial activity & soluble markers
 
					✓																							
Device insertion																												
OPK dispensed																												
Visit OP2: CMC:																												
Note device position																												
Cervical mucus for FG, pH, midcycle													√															
characteristics, and the presence of sperm													V															

 
Vaginal sample for pH, FG, & presence of sperm
 
																												
Visit OP3: PCT:																												
• Questionnaire.																												
Note device position.																												

 
Cervical mucus for FG, pH, midcycle
 
																												
characteristics, and the presence of sperm																												

 
Vaginal samples for FG, pH, & presence of sperm
 
																												

 
At non-EVMS sites: vaginal samples for antibacterial activity and soluble markers
 
														✓														
EVMS only:																												
o At 0.5, 1, 2, 4, & 6 hrs, if possible:																												

 
Vaginal samples for FG & pH
 
																												
o At 6 hrs, if possible:																												

 
Vaginal sample(s) for antibacterial
 
																												
activity and soluble markers																												
Visit OP4: 24 hrs after PCT:																												
Note device position.															✓													

 
Vaginal samples for FG & pH
 
																												
Visit OP5:																												
Note device position.																												
• Vaginal samples for FG, pH, Nugent score,																												✓
microflora, antibacterial activity, & soluble																												
markers																												
Device removed																												

Version: 06.00 (FINAL) Date: June 13, 2019

Colposcopy																	

 
Cervical mucus for FG & pH
 
If 1st Ovaprene PCT, dispense OPK & condoms as needed
 
If 2nd Ovaprene PCT, contact in 7-10 days and exit if no AEs requiring follow-up
 
																	
Sex restrictions	Condo	ms	'		No sex activity ejacula	/ & no r	_	Sex	No sex/ vag act	Condoms lubricated with something other than nonxynol-9 must be used. No sex or other vaginal activity is permitted in the 72 hours prior to the final visit in the cycle.							

Version: 06.00 (FINAL) Date: June 13, 2019

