Safety data are also needed. Treatment-emergent systemic and genital adverse events (AEs) will be collected from both the female participants and their male partners, via report from the female participants. Additional information on systemic effects in the female participant will be collected in the form of standard safety labs (complete blood count and serum chemistries) as well as labs that are specific to Ovaprene™. The latter will include serum ferritin, a protein that is involved in iron storage and which becomes elevated in situations of iron overload. While the likelihood of iron overload developing from the small amount of iron in Ovaprene™ (569.8 mg, ¹ the maximum amount that could be released over an entire cycle of use, as compared with 325 mg daily included in many multivitamins) is minimal, systemic safety will be documented.

Additional genital safety data will come from findings via pelvic exam, including colposcopy, and changes in Nugent score and microflora. The ability of the product to maintain vaginal innate immunity will be assessed using antibacterial activity in the CVF and soluble markers of inflammation in CVF. Any potential colonization of the product by *Staphylococcus aureus* or group A Streptococcus, the organisms associated with Toxic Shock Syndrome, will be assessed on devices that have been worn over a cycle of use.

Finally, a product that is unacceptable to women or their partners will not have commercial potential. This study will collect acceptability information from both partners. It will also assess the proportion of women for whom Ovaprene™ will fit and those who can insert, position, and remove the device with only written instructions. It will also determine where, in relation to the cervix, the device comes to reside after insertion and after sex, and the relationship of that location to PCT results, safety, and acceptability. The study described here will have as its objectives the collection of all these types of data − changes in PCT results due to device use, release, safety, acceptability, and fit.

Version: 06.00 (FINAL) Date: June 13, 2019

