# b) Visit 3 (BP2) – the PCT visit, 2-3 hours after intercourse and within 27 hours of the CMC:

The participant will return to the clinic 2-3 hours after coitus ends and within approximately 27 hours of the mucus check visit.

- Diary review, AEs, medications, and indications for a directed physical exam, wet mount, and other tests will be managed as described for Visit 2 (BP1).
- The participant will undergo a pelvic exam:
  - o Signs of irritation of the external genitalia, cervix, and vagina, as observed with the naked eye, will be noted.
  - o Cervical mucus will be examined for pH, midcycle characteristics, and the presence of sperm (see **Appendix 2**).

g These will serve as baseline measurements for comparison with those obtained after device insertion during Visit OS1. The alternative would be to collect baseline measurements before device insertion at Visit OS1, but the collection technique (vaginal lavage) is likely to affect subsequent samples taken at that visit.

<sup>h "Other vaginal activity" includes insertion of vaginal medications/products other than the study product (prescription or over-the-counter), as well as insertion of sex toys, fingers, or anything else into the vagina. Tampons may be used during all days of menses in the Baseline PCT and Caya PCT cycles, but only during the first three days of menses in Ovaprene cycles.

Version: 06.00 (FINAL) Date: June 13, 2019

- o Vaginal sample(s) will be collected for pH and the presence of sperm.
- At sites other than EVMS, vaginal samples will be collected for microflora, antibacterial activity, and soluble markers.i
   Baseline PCT results will be interpreted and managed as listed in **Appendix 3**. A successful baseline PCT will show thin mucus containing an average of >5 progressively motile sperm per HPF.
- At the EVMS site only:
  - o 0.5, 1, 2, 4, and 6 hours after the PCT:
    - Cervical mucus will be collected for assessment of pH.
    - Vaginal sample(s) will be collected for assessment of pH.
  - o 6 hours after the PCT, if possible:
    - Vaginal sample(s) will be collected for baseline levels of microflora, antibacterial activity, and soluble markers.k
- The participant will be instructed to refrain from intercourse and other vaginal activity until after Visit BP3, 24 hours after Visit BP2.

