**Table 14: Endpoint Evaluations** 

	Goal	Baseline	Compared with
Changes in CBC,* chemistries,* and ferritin, colposcopy*	Assess effect of device on these endpoints after one cycle of use in the absence of sex, compared with before insertion	OS1	OS5
Nugent score,* vaginal microflora, vaginal antibacterial	Assess effect of device on these endpoints over one cycle, in the absence of sex, compared with before insertion	OS1	OS2, OS3, OS4, OS5
activity, and soluble markers	Assess effect of device on these endpoints after the device has been in place for one cycle, with multiple acts of sex up until 72 hours before the last visit, compared with before insertion	OP1	OP5
Vaginal antibacterial activity and soluble markers of inflammation	Assess effect of device insertion on these markers, in the absence of sex	BP1	OS1 after device insertion Baseline sample cannot be collected before device insertion at this visit because collection technique (vaginal lavage) is likely to affect subsequent samples taken at this visit.
	Assess effect of device on these markers after sex, compared with after sex with no device in place	BP2	OP3
	Assess effect of device on these markers after sex, compared with before sex	OP1	OP3

\* Also done at Visit 1 to establish eligibility

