# APPENDIX 1. SCHEDULE OF ASSESSMENTS

X = required O = if indicated

The pelvic exam procedures are listed in the recommended sequence of collection.

The pelvic exam procedures are listed in ti	ic recomme	lucu 3	cquem		Oncer	J11.											
	Screening	BP1	BP2	BP3	CP1	CP2	OS1	OS2	OS3	OS4	OS5	OP1	OP2	OP3	OP4	OP5	UNS
Informed Consent (also male, if																	
required)	Χ																
Assign Subject Number	Χ																
Demographics	Х																
Assess eligibility	Χ	Χ															
Enroll participant				Χ													
Medical/Obstetrical History 	Χ																Х
Directed Physical Exam 	0	0	0	0	0	0	0	0	0	0	0	0	0	0	0	0	Х
Height/Weight	Χ																Х
HIV 	Χ																Х
Urine Pregnancy Test	Х																Х
Urinalysis 	0	0	0	0	0	0	0	0	0	0	0	0	0	0	0	0	Х
CBC, Chemistry, Serum Ferritin	Χ						Χ				Χ						Х
Review Diary Entries		Χ	Х	Χ	Χ	Χ	Χ	Х	Х	Х	Х	Χ	Х	Χ	Χ	Χ	Х
AEs, Concomitant Medications		Χ	Х	Χ	Χ	Х	Χ	Х	Х	Х	Х	Χ	Х	Х	Х	Χ	Х
Acceptability Questionnaire											Х			Х			
Note device position by digital exam								Χ	Χ	Χ	Χ		Х	Х	Χ	Χ	Х
Pelvic exam - note irritation seen with																	
naked eye		Χ	Χ	Χ	Χ	Χ		Χ	Χ	Χ			Χ	Χ	Χ	Χ	Х
Exam of external genitalia, by naked																	
eye & colposcopy	X						Х				Х	Х				Х	Х
Colposcopic Exam - insert speculum, do naked eye exam of visible vaginal																	l
epithelium	Х						Х				Х	Х				Х	Х
Note device position with speculum in																	
place								Χ	Х	Χ	Х		Х	Х	Х	Х	Х
Vaginal pool - Trich test	Х																Х
Vaginal pool - Wet mount 	X	0	0	0	0	0	0	0	0	0	0	0	0	0	0	0	Х
Vaginal pool - ferrous gluconate							X 	Х	Х	Х	Х	Χ	Х	X 	Х	Χ	Χ

Version: 06.00 (FINAL) Date: June 13, 2019

Vaginal pool - Vaginal sperm evaluation		Х	Х		Х	Х							Х	Х			Х
Vaginal lateral wall - pH	Х	Χ	X 	Χ			X 	Χ	Х	Х	Χ	Х	Х	X 	Χ	Χ	Х
Vaginal lateral wall - Nugent Score	Χ						Χ	Χ	Х	Χ	Χ	Χ				Χ	Χ
Vaginal lateral wall - microflora		Χ	Χ	Χ			Χ	Χ	Χ	Х	Χ	Χ				Χ	Х
Vaginal lateral wall - back-up swab for																	
antibacterial activity, soluble markers		Χ	X 				X 	Χ	Χ	Χ	Χ	Χ		X 		Χ	Χ
Displace Ovaprene temporarily for																	1
specimen collection if necessary									Х		Х		Х	Х		Χ	Х
Cervical pH		Х	X 	Χ			Х		Х		Х	Х	Х	Х		Χ	Χ
Cervical mucus by pipette - midcycle		V	V		V	V							· ·	V			V

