characteristics and sperm  Cervical mucus by pipette - ferrous		Х	Х		Х	Х							Х	Х			Х
gluconate									Х		Х	Х	Х	Х		Х	х
Replace Ovaprene if displaced									X		X		X	X		X	X
Vaginal lavage - antibacterial activity,											7.			,			
soluble markers		Χ	X 				$X^{11}$	Χ	Х	Х	Х	Х		X 		Х	Х
Remove Ovaprene - swab for staph																	
aureus and store											Χ					Χ	Χ
Colpo exam of cervix under																	
magnification	Х						Χ				Χ	Χ				Χ	Х
Pap Test 	Х									1							
GC/CT if using cervical specimens 	Χ																Χ
Colpo exam of fornices and of vagina																	
(latter while removing speculum)	Х						Х				Х	Х				Χ	Х
Ovaprene Fit Test				Χ													
Caya Fit Test	Х																Х
Insert Ovaprene 							Χ					Χ					Χ
Remove Caya						Χ											Χ
Dispense Caya					Χ												
Explain Trials.ai	Х																
Dispense OPK Kit	Χ			Χ				Χ				Х				Χ	Χ
Dispense condoms	Χ			Χ							0					0	Χ

<sup>1 Medical and Obstetrical history will include contraceptive and gynecological history also.

Version: 06.00 (FINAL) Date: June 13, 2019

<sup>2 A physical exam will be performed if the history is significant for a medical condition. The directed physical exam can be performed at any visit.

<sup>3 HIV testing will be performed on all female participants. HIV testing is available for the male partners, if requested.

<sup>4 Urinalysis is only required if participant is symptomatic for UTI. Treat UTI with oral meds. If Visit 1, continue participant. If after Visit 1, reschedule visit.

<sup>5 The pelvic exam at every visit should look for signs of irritation of the external genitalia, cervix and vagina, as seen with the naked eye. A Pap Test will be performed at Visit 1, if necessary, consistent with the standard medical practice as outlined in the study manual.

<sup>6 **STI**: treat with oral meds and do not continue participant.

<sup>7 **Candidiasis**: treat with oral meds. If Visit 1, continue participant. If after Visit 1, reschedule visit. **BV**: treat with oral meds. If diagnosed at Visit 1, continue participant. If diagnosed after Visit 1, do not continue participant.

<sup>8 EVMS only: Cervical mucus pH will also be tested at 0.5, 1, 2, 4, and 6 hour time points, if possible.

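### At OS5 and OP5 the recommended sequence lavages the vagina with Ovaprene in place just before the device is removed and swabbed, which puts the device-colonisation endpoint (3f) at risk of bias of unknown size

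*Protocol*

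**What the plan says.** Appendix 1 of the protocol states that "The pelvic exam procedures are listed in the recommended sequence of collection". For OS5 and OP5 the relevant rows run in this order:

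1. Displace the device temporarily if specimen collection needs it.
2. Take cervical pH and cervical mucus.
3. "Replace Ovaprene if displaced".
4. "Vaginal lavage - antibacterial activity" and soluble markers.
5. "Remove Ovaprene - swab for staph" aureus, and store.

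The lavage row and the removal-and-swab row are both marked at OS5 and OP5. SAP 4.1 lists the rows in the same order. The visit text agrees as far as it goes: in 9.4.1 e) and 9.5.1 e) the antibacterial and soluble-marker samples are listed before device removal. At OP5 the removal line reads only "Ovaprene™ will be removed and stored for later analysis", with no mention of a swab.

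On lavage itself, footnote g in 9.2.1 explains why the baseline for the OS1 post-insertion samples is taken at BP1: "the collection technique (vaginal lavage) is likely to affect subsequent samples taken at that visit". Table 14 gives the same reason: "collection technique (vaginal lavage) is likely to affect subsequent samples taken at this visit".

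The swab serves endpoint 3f, the presence of S. aureus or group A Streptococcus on worn devices. The Introduction links these organisms to Toxic Shock Syndrome and says colonisation "will be assessed on devices that have been worn over a cycle of use". SAP 3.7.6 leaves the S. aureus assessment to the vendor, whose analysis is appended to the clinical study report.

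**The concern.** A site that follows the recommended order swabs a device that has just been through a lavage. The protocol treats lavage carry-over as serious enough to move one baseline to a different cycle. It does not apply the same caution to the device swab, and does not say why the swab would be unaffected.

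Endpoint 3f is the only planned measure of organisms on the device. If lavage washes off or dilutes organisms, fewer colonised devices will be found. For a device worn for weeks, a falsely clean result is the error that matters most. Even if lavage acted the other way, by moving vaginal organisms onto the ring, the swab would no longer describe the device as worn.

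**Working it through.** **Order of steps.** Appendix 1 puts the device back before the lavage row, so the device is in the vagina during lavage. Removal and swabbing are the next row. Both rows are marked at OS5 and OP5, so the sequence affects the end-of-cycle device in all three Ovaprene cycles.

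**Carry-over.** Footnote g and Table 14 were both written about OS1. The reason they give is the collection technique, which is the same at OS5 and OP5. Neither statement gives a direction or a size, and neither mentions a device swab. No other text in the protocol or SAP addresses the effect of lavage on the swab.

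**Size.** The documents state no carriage rate, swab sensitivity or rinse effect, so there is no plan figure to reproduce. Two illustrations follow; both assume that lavage lowers recovery.

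*Illustration 1: expected positive devices.* From the documents: about 25 completers (Protocol 14.1) and 3 Ovaprene cycles each, so 25 × 3 = 75 devices. Assumed: 10% truly colonised (7.5 devices), a Poisson mean of m recoverable organisms per swab of a colonised device, and a fraction f removed by lavage. Detection = 1 − exp(−m(1 − f)); expected positives = 7.5 × detection.

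| f | Detection, m = 3 | Expected positives, m = 3 | Detection, m = 10 |
|---|---|---|---|
| 0 | 95.0% | 7.1 | 100% |
| 0.1 | 93.3% | 7.0 | 100% |
| 0.2 | 90.9% | 6.8 | 100% |
| 0.5 | 77.7% | 5.8 | 99% |
| 0.8 | 45.1% | 3.4 | 86% |
| 0.9 | 25.9% | 1.9 | 63% |

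For example, with m = 3 and f = 0.5: 1 − exp(−1.5) = 0.777, and 7.5 × 0.777 = 5.8.

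*Illustration 2: chance of seeing no positive device.* Take one device per woman, n = 25, true carriage p, and relative swab sensitivity s after lavage (p and s assumed). P(no positives) = (1 − ps)^25.

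| p | s = 1.0 | s = 0.8 | s = 0.5 |
|---|---|---|---|
| 5% | 27.7% | 36.0% | 53.1% |
| 10% | 7.2% | 12.4% | 27.7% |
| 20% | 0.4% | 1.3% | 7.2% |

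If 0 of 25 were observed, the exact two-sided 95% upper limit is 1 − 0.025^(1/25) = 13.7%. Dividing by s to allow for lost sensitivity gives 17.1% at s = 0.8 and 27.4% at s = 0.5.

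The effect runs from negligible to large, and the assumed inputs alone decide which.

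**The case against.** The strongest objection is that the documents do not show a bias. They give no lavage volume, target site or swab technique, and they refer other procedural detail to a Study Procedures Manual that is not part of them. Lavage might even carry organisms onto the ring. The carry-over warning was written for OS1 samples, and at OS1 the non-EVMS sites do take antibacterial and soluble-marker samples before insertion, so it is not a general ban on lavage. The Appendix 1 order is recommended, not required. The visit text is weak support, because it lists cervical mucus after device removal while Appendix 1 collects it before. All of this stands. It limits the claim to a risk of bias. It does not remove the mismatch between the recommended order and the protocol's own reasoning about lavage.

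A reader might infer that rinsing can only lower recovery and that the endpoint is therefore biased towards negative. The documents do not support that: under-detection is plausible, but its direction is an inference.

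A reader might also object that the end-of-cycle lavage is taken with the device in while the OP1 baseline is taken without it. That is not a defect. Table 14 sets out to compare the device in place with the state before insertion.

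A further objection concerns cost. If the device is taken out before lavage, the OS5 lavage becomes the only post-insertion one in the safety cycle taken with the device out, which could disturb endpoint 3e. That is a real trade-off, and swabbing at the displacement step avoids it. Timing also counts. This protocol version is dated June 13, 2019, and the Synopsis estimates last completion on September 1, 2019, so a change would reach only the later devices.

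**Conclusion.** The point holds as a risk of bias. If the recommended order is followed, the swab for endpoint 3f comes from a device that has just been through a lavage. The protocol says lavage is likely to affect later samples at the same visit, and neither document exempts the swab or corrects for it. Under-detection is the plausible direction.

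No size can be derived from the documents. With 7.5 colonised devices and m = 3, expected positives run from 7.0 (10% rinsed off) to 1.9 (90% rinsed off), against 7.1 with no rinse. With m = 10, halving the organisms leaves detection at 99%. These figures rest on assumed carriage, organism load and rinse fraction, and on sites keeping to the recommended order. They should not be read as an estimate of what the trial will lose.

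**What to change.** In Protocol Appendix 1, SAP 4.1, and Protocol 9.4.1 e) and 9.5.1 e), put the device swab before the lavage at OS5 and OP5. There are two ways:

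- **Swab at the existing displacement step, then replace the device and lavage.** This keeps the OS5 lavage comparable with OS2 to OS4. The displacement row is conditional, so the text must require the swab whether or not the cervical samples needed displacement. The sponsor should also confirm that the swab technique works on a displaced device.
- **Remove and swab the device, then lavage.** This saves the replacement step. Its small downside is that the OS5 lavage is then taken with the device out, unlike OS2 to OS4.

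Record for each device whether the swab came before or after lavage. Ask the vendor to report the two groups separately in the analysis appended to the clinical study report. That request belongs with the vendor, because SAP 3.7.6 does not analyse this endpoint. If the sponsor keeps the current order, the protocol should say why lavage does not affect the swab.

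While editing these places, align the position of cervical mucus collection between the visit text and Appendix 1. Also name group A Streptococcus in the swab row, which now lists only S. aureus although endpoint 3f names both.

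The change needs no extra sample or visit. It does need an amendment with sponsor and IRB approval (Protocol 19.1). Where devices have already been swabbed, recording the order and splitting the report is the part that still helps.
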